The study includes a screening period of up to 35 days (with 2 screening visits) and a treatment period of approximately 12 months (52 ± 2 weeks) (with 6 treatment/observational visits) plus an additional follow-up at a pulmonary laboratory 4 to 5 weeks after the last treatment/observational visit. A longer screening period may be permitted with approval from the Sponsor. Planned treatment/observational visits will occur at 0 (pre-dose, baseline) and approximately 1, 3, 6, 9, and 12 months. For the CVT-301 treatment group, these visits will be treatment visits and for the observational cohort, these will be observational visits. All patients, regardless of treatment group, will be required to attend all of the screening visits and all of the treatment/observational visits. Assessments for DLco will be performed at a pulmonary laboratory outside of the clinic prior to the TV/OV1, within 2 weeks prior to the 3-, 6-, 9-, and 12-month visits, and 4 to 5 weeks after TV/OV6.

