8.2. Exclusion Criteria

Patients meeting any of the following exclusion criteria at screening will not be enrolled in the study:

1. Patients who have dyskinesia of a severity that would significantly interfere with their ability to participate or perform study procedures.
2. Pregnant or lactating females or females wishing to become pregnant.
3. Patients who have any known contraindication to the use of LD, including a history of malignant melanoma or a history of narrow-angle glaucoma.
4. Patients who have had previous surgery for PD (including but not limited to deep brain stimulation [DBS] or cell transplantation).
5. Patients with a history of psychotic symptoms requiring treatment, or suicide ideation or attempt within the prior 12 months (stable regimens [for at least 4 weeks prior to SV1] of anti-depressant and certain low-dose atypical antipsychotic medications are permitted in case they are indicated to treat symptoms other than psychotic symptoms).
6. Patients who have cancer with the exception of the following: basal cell carcinoma or successfully treated squamous cell carcinoma of the skin; cervical carcinoma in situ; prostatic carcinoma in situ; or other malignancies curatively treated and with no evidence of disease recurrence for at least 3 years.
7. Patients taking certain prohibited medications (see [Section 9.4.2](#)).
8. Patients with a history of drug or alcohol abuse within the prior 12 months.
9. Patients with chronic obstructive pulmonary disease (COPD), asthma, or other chronic respiratory disease within the last 5 years.

10. Patients with any contraindication to performing routine spirometry or who are unable to perform a spirometry maneuver (see [Appendix 20](#) for a list of contraindications).
11. Patients with a current history of *symptomatic* orthostatic hypotension despite adequate treatment.
12. Patients with any condition that in the investigator's opinion would make patients unsuitable or interfere with their participation in the study. Potential issues of concern should be raised to the medical monitor during eligibility review.
13. Patients who have any clinically significant abnormality or finding from examination, tests, or history that may compromise patient safety.
14. Patients who have been treated with an investigational drug within 4 weeks or 5 half-lives (whichever is longer) prior to the beginning of the screening period (this includes investigational formulations of marketed products).

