10.3.2. Treatment Visit/Observational Visit 1 (at least 7 days after SV2)

10.3.2.1. Treatment Visit 1 for the CVT-301 Treatment Group

Patients will complete the Screening ON/OFF Episodes Log and PD Diary for the 3 consecutive days prior to TV1.

Patients will report to the clinic after having taken their usual PD medications prior to the visit. The timing of arrival for TV1 should be scheduled to increase the likelihood that patients will be in the ON state upon arrival (i.e., they should arrive to the clinic as shortly as feasible after taking their standard oral PD medications at home). Patients will bring to the clinic all of their usual prescribed PD medications.

On Arrival to the Clinic

The following list is a suggested schedule for this visit:

- Collect, review, sign, and date the PD Diary and Screening ON/OFF Episodes Log and document whether these were completed correctly.
- Confirm that the DLco assessment has been performed. If the DLco assessment has not been completed prior to the visit, the study visit must be re-scheduled.
- Record the time that patients took their usual PD medications prior to the visit.
- Record any changes in the usual PD medication dose/regimen.
- Record all concomitant medications.
- Perform the PDQ-39 in an ON state.
- Perform a brief physical examination.
- Patients will complete the UPDRS Part 2 and S&E ADL scales (preferably in the ON state).
- Patients will complete the UPDRS Part 4 (Questions 32-35 and 36-39).
- Perform a 12-lead ECG.
- Record standard and orthostatic BP and HR. Record RR.
- Perform spirometry (preferably performed in the ON state; record the patient's motor state on the spirometry source record).
- Collect blood for clinical laboratory tests including serum pregnancy test, if applicable. Document fasting status.
- Perform the baseline assessments using the C-SSRS, Epworth Sleepiness Scale, and the QUIP.
- Distribute the PD Diary and review instructions for completion for recording time asleep, time OFF, time ON without dyskinesia, time ON with non-troublesome

dyskinesia, and time ON with troublesome dyskinesia (to be completed for the 3 consecutive days prior to TV2, TV3, TV4, TV5, and TV/6).

- Distribute the Inhaled Dosing Log and review instructions for completion for recording the number of times the inhaler was used and the number of capsules used for each inhalation treatment (to be completed daily throughout the 12-month treatment period).

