11.1.12.2. Columbia-Suicidality Severity Rating Scale

The C-SSRS is a measure of suicidal ideation and behavior. The rating scale has 4 general categories: suicidal ideation, intensity of ideation, suicidal behavior, and actual attempts. An initial baseline version will be given at TV/OV1, and a “since last visit” version will be given at all treatment visits to detect any emergence of suicidal ideation or behavior. The clinic staff should address any emerging neuropsychiatric needs in the event that the C-SSRS indicates active suicidal ideation.

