- Spirometry: FEV1, FVC, and the FEV1/FVC ratio during specified treatment visits and over the course of the study will be evaluated. The number and proportion of patients with pre-specified changes in spirometry parameters will be tabulated.

Changes from baseline to follow-up in the rating scales for assessing suicidality, somnolence, and impulse control disorders will be summarized descriptively.

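### The C-SSRS is to be summarised as change from baseline although its baseline and follow-up forms cover different recall periods; a count of on-study ideation and behaviour would match its stated purpose better

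*Protocol*

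**What the plan says.** The C-SSRS is the only suicidality scale in the protocol and is named in a secondary safety objective (Section 6). Section 11.1.12.2 sets out how it is given: "An initial baseline version will be given at TV/OV1, and a “since last visit” version will be given at all treatment visits". The purpose of the later form is stated as "to detect any emergence of suicidal ideation or behavior". The instrument is described by category, with no total score: "The rating scale has 4 general categories: suicidal ideation, intensity of ideation, suicidal behavior, and actual attempts".

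For analysis, Section 12.5 has one sentence covering three scales: "Changes from baseline to follow-up in the rating scales for assessing suicidality, somnolence, and impulse control disorders will be summarized descriptively". The synopsis carries the same sentence. Section 12.5 names no tabulation of suicidal ideation or behaviour arising on study.

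Two other places matter. Exclusion criterion 5 in Section 8.2 bars "suicide ideation or attempt within the prior 12 months", so a patient with an older history can enter. Section 7 fixes the schedule: "Planned treatment/observational visits will occur at 0 (pre-dose, baseline) and approximately 1, 3, 6, 9, and 12 months". The protocol does not say how far back the baseline form looks.

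**The concern.** A change from baseline is easy to interpret when the same question about the same length of time is asked twice. The protocol gives no sign of separate baseline and follow-up forms for the Epworth scale or the QUIP. For the C-SSRS it expressly provides two. The baseline form has to describe time before the study, and each later form describes only the interval since the previous visit. Comparing them mixes a difference in the patient with a difference in the window.

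The summary also answers a different question from the one the later form is there to answer. That form is meant to show whether ideation or behaviour appeared on study. Elsewhere Section 12.5 uses summaries of that kind: adverse events are counted as treatment-emergent, and spirometry is tabulated as proportions of patients crossing a threshold. The C-SSRS gets neither. What is at stake is how clearly one component of a secondary safety objective is reported, not the care of individual patients.

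**Working it through.** The protocol states no figure on this point, so there is none to reproduce. The check sets the sections side by side and then follows the consequence.

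**1. Recall windows at follow-up.** The headings of Section 10.3 place TV/OV2 to TV/OV6 at nominal weeks 4, 12, 24, 36 and 52 after TV/OV1. A since-last-visit form covers the gap to the previous visit:

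| Visit | Calculation | Window (weeks) |
|---|---|---|
| TV/OV2 | 4 − 0 | 4 |
| TV/OV3 | 12 − 4 | 8 |
| TV/OV4 | 24 − 12 | 12 |
| TV/OV5 | 36 − 24 | 12 |
| TV/OV6 | 52 − 36 | 16 |

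The longest window is four times the shortest. With a constant rate of ideation, later visits would tend to show more of it simply because they cover more time. This holds whatever the baseline look-back is. A side point: the synopsis list for TV/OV2 omits the C-SSRS, while Sections 10.3.4.1 and 10.3.4.2 and Appendices 6 and 7 include it. If it were skipped there, the TV/OV3 window would be 12 weeks instead of 8.

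**2. Effect on a single patient.** Assumptions, not in the protocol: ideation is graded 0 to 5, and change = on-study level − baseline level.

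| Patient | Look-back over 12 months | Look-back 12 months or less | On-study level |
|---|---|---|---|
| Old level 4, none on study | 0 − 4 = −4 | 0 − 0 = 0 | 0 |
| Old level 4, recurs at 2 | 2 − 4 = −2 | 2 − 0 = +2 | 2 |
| Old level 4, recurs at 4 | 4 − 4 = 0 | 4 − 0 = +4 | 4 |
| No history, new level 2 | 2 − 0 = +2 | 2 − 0 = +2 | 2 |

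Here old means more than 12 months before screening. In the short look-back column the baseline is about zero because exclusion criterion 5 removes patients with ideation in that period. The change then equals the on-study level and the artefact goes away. With the long look-back, the two recurrences show as −2 and 0.

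**3. Effect on a group mean, as illustration only.** Assume a long look-back, a share *h* of the group with old ideation at level 3, and a share *e* with on-study ideation at level 2. Mean change = 2*e* − 3*h*; the on-study mean alone is 2*e*. With *e* = 3%:

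- *h* = 0: 0.06 − 0 = +0.06
- *h* = 2%: 0.06 − 0.06 = 0.00
- *h* = 5%: 0.06 − 0.15 = −0.09
- *h* = 10%: 0.06 − 0.30 = −0.24

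The on-study value is +0.06 throughout. This shows the direction of the effect; neither *h* nor *e* is given in the protocol.

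**The case against.** The strongest reply is that the protocol does not prescribe the calculation used above. It defines no score, no subtraction and no category of improved. Since Section 11.1.12.2 describes the scale by category, a descriptive summary of change could well be a shift table of baseline against on-study category, and that would leave every recurrence visible. This stands: the misreading in steps 2 and 3 needs a difference score, which is one possible reading and not the stated one.

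The look-back is also unknown, and with 12 months or less the main artefact all but disappears. This stands too.

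A reader might infer that the plan hides suicidality on treatment, or biases the results towards improvement by a known amount. The documents do not support that. Section 12 promises that all data will be listed. Section 11.1.8 treats any symptom that emerges or worsens as an adverse event, and Section 12.5 tabulates treatment-emergent events by group, although nothing makes a positive C-SSRS answer an adverse event automatically. Under Section 11.1.12.2, clinic staff respond to active ideation regardless of any table. Among randomised patients the recall effect should be similar in the two groups, so it would not by itself create a difference between them.

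Finally, Section 12 leaves technical detail to the SAP, which prevails over the protocol where they differ. That allows the SAP to correct the sentence but does not make it fit the instrument: the protocol names a summary, in two places, and it is not the one that the follow-up form is designed for.

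**Conclusion.** The point holds in a limited form. What rests on the text alone is that the named summary compares forms with different recall periods, that the follow-up windows themselves run from about 4 to 16 weeks, and that no count of on-study emergence is named although emergence is the form's stated purpose.

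That old ideation reads as improvement, or recurrence as no increase, is conditional on two things the protocol does not state: a baseline look-back of more than 12 months, and change taken as a difference. If either fails, the effect is near zero or does not arise. No number of affected patients can be given, because the protocol supplies neither the share with a history nor the on-study rate. The weight is minor: the summary is descriptive, feeds no test or decision rule, concerns one component of a secondary safety objective, and is partly backed up by adverse event tables and listings.

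**What to change.** In Section 12.5 and the synopsis, remove suicidality from the change-from-baseline sentence and leave the sentence as it is for the Epworth scale and the QUIP. Add for the C-SSRS: by group, the number and proportion of patients with any suicidal ideation (by category) or any suicidal behaviour on a since-last-visit form after TV/OV1, for all patients and for those with none recorded at baseline. A shift table of baseline category against worst on-study category would serve equally well. Counting over the whole period after TV/OV1 also avoids comparing visits with unequal windows.

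The data are already collected. The cost is one reworded sentence in two places and one extra table.

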12.5.1. Interim Safety Data Review

Safety data will be reviewed by a DSMC that will include relevant medical experts (including a neurologist and pulmonologist), an independent statistician, and additional representatives (as will be defined in the DSMC Charter). Safety data, including but not limited to AEs, spirometry, vital signs, and ECG data will be reviewed. The safety review will be documented in a DSMC Charter prior to the start of the study. In the event that potential safety issues are identified, the committee may recommend modification of the study design or study termination, which will be communicated promptly with investigators, IRBs, IECs, and regulatory agencies, in accordance with legal and regulatory requirements. Interim analyses, which will not affect study conduct, may be performed to support regulatory submissions. These analyses will be described in the SAP.

12.6. Exploratory Efficacy Analysis

The derivation of the exploratory efficacy variables will be defined in detail in the SAP.

The changes from baseline in continuous exploratory efficacy variables will be estimated using an MMRM. The model will include visit and the stratification variables (Hoehn and Yahr stage and screening FEV1 and/or FEV1/FVC) as fixed factors. The baseline value will be used as a covariate. For variables which do not have a pre-treatment baseline assessment, OFF-state baseline UPDRS Part 3 score will be used as the baseline covariate. An unstructured covariance structure will be applied for the MMRM. In case the model will not converge with the unstructured covariance structure, compound symmetry will be used instead.

The sensitivity analyses will be specified in the SAP. Sensitivity analysis will be performed at least for the method to handle missing data (e.g., last observation carried forward, pattern mixture model using multiple imputation instead of MMRM), definition of analysis population (e.g., patients completing the study instead of observed cases), and statistical method (e.g., analysis of covariance [ANCOVA] models separately for each visit instead of MMRM).

The categorical data will be primarily evaluated descriptively. Each visit will be evaluated separately for the categorical endpoints.

The exploratory efficacy data collected from the patients in the observational cohort will be summarized with descriptive statistics.

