9.2. Randomization and Administration of Study Treatment

9.2.1. Randomization and Assignment of Study Treatment

Following completion of SV2 and prior to randomization, the patients' eligibility criteria will be reviewed by delegated staff. Upon confirmation of eligibility, the site will randomize an eligible patient using the Interactive Web Response System (IWRS). Sites must allow 7 business days between time of randomization and the first treatment visit (TV1) to allow time for drug to be shipped and received.

Eligible patients will be randomized in a 2:1 ratio to CVT-301 treatment (CVT-301 50 mg PD FPD) or the observational cohort. Randomization will be differentiated by the patient's Hoehn and Yahr stage (<2.5 versus ≥2.5) to balance the severity of disease across each treatment group and by screening spirometry (FEV1 <60% of predicted or FEV1/FVC ratio <70% versus FEV1 ≥60% of predicted and FEV1/FVC ratio ≥70%). Patients who previously completed the CVT-301-002 and CVT-301-003 studies will be assigned only to the CVT-301 treatment group. The study is an open-label study, so patients and clinical staff will not be blinded to study group assignment.

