12. Measure standard vital signs (BP, HR, and RR) and orthostatic vital signs (BP and HR). Standard vital signs should be taken after the patient has rested in a supine or semi-supine position for at least 5 minutes, and orthostatic vital signs should be taken after the patient has been standing for 2 minutes (see [Section 11.1.2](#) for suggested detailed procedures).
13. Perform spirometry to measure FEV1, FVC, and FEV1/FVC ratio to assess lung function (this must be performed with the patient in the ON state).
14. Perform UPDRS Part 3 in an ON state.
15. Train patients on how to assess their ON and OFF states and how to record their waking ON/OFF status in a screening PD Diary (time OFF, time ON without dyskinesia, time ON with non-troublesome dyskinesia, time ON with troublesome dyskinesia, and time asleep).
16. Perform concordance testing with the patients (while in the ON and OFF states) for recognizing different ON/OFF states and recording them appropriately in the PD Diary. Patients will be tested for competence at self-rating and must be within 75% concordance with the ratings of the examiner (at least 3 out of 4 half-hour sessions over the course of 2 hours); if concordance is not reached, the observation period may be extended for an additional 2 hours to obtain agreement on at least 6 of 8 half-hour sessions. The same training and testing may be repeated at an unscheduled visit between SV1 and SV2 or at SV2. If patients return for an unscheduled visit between SV1 and SV2 for concordance training and testing, the visit must occur more than 3 days prior to SV2. If patients do not achieve 75% concordance by the end of SV2, they will be considered screen failures.
17. Introduce the inhaler and perform inhaler training using sham capsules with the CVT-301 inhaler while in the ON state.
18. Take samples for clinical laboratory tests, including a serum pregnancy test for females of childbearing potential (see [Appendix 17](#) for a list of laboratory parameters assessed). Patients do not need to be in a fasted state at the time of the laboratory sample; however, fasted status will be documented (with fasting defined as at least 4 hours following the last meal or snack).
19. Patients will remain in the clinic and further PD medications will be withheld until they turn into an OFF state.

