12.3. Definition of Baseline

In all statistical analyses of the CVT-301 treatment group, the visit at which the CVT-301 treatment was initiated will be used as the baseline. However, for all patients who were included in the CVT-301-002 or CVT-301-003 studies, TV/OV1 of the CVT-301-005 study will be used as baseline. For the observational cohort, the assessments at TV/OV1 will be used as baseline.

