12.5. Safety Analysis

The disposition of the patients will be summarized by tabulating the number of screened, randomized, completed, and discontinued patients. The reasons for premature discontinuations will be tabulated.

The extent of exposure to study treatment will be summarized for the patients who received CVT-301 treatment. The time period between TV/OV1 and TV/OV6 (or Early Withdrawal Visit) will be used as the measure of extent of exposure for the patients randomized to the observational cohort. Adverse events will be tabulated by treatment group according to the Medical Dictionary for Regulatory Activities (MedDRA). Study-emergent and treatment-emergent adverse events (TEAEs) will be summarized by body system and preferred term. For patients in the observational cohort, the AEs collected between TV/OV1 and TV/OV6 (or Early Withdrawal Visit) will be considered as TEAEs. Furthermore, the time of onset of the TEAEs will be summarized.

For vital signs, ECG parameters, spirometry measurements, and DLco, the changes from pre-dose to post-dose assessments of the corresponding day will be calculated and described using descriptive statistics. For spirometry, DLco, and safety laboratory variables, the differences in pre-dose values between the study days will be described. Furthermore, the changes in the spirometry values and difference between the groups will be estimated using a Mixed Model for Repeated Measurements (MMRM) similar to the one used for the efficacy variables. The proportion of patients with abnormal spirometry values will be tabulated using different criteria for the threshold (e.g., at least 10% or 20% change from baseline at any single visit, at least 10% or 20% change from baseline on at least 2 consecutive visits). The proportions of patients meeting ATS quality criteria (and also for those 'rejected') will be summarized. All spirometry analyses will be performed both for all patients regardless of the ATS quality criteria and separately excluding the assessments not meeting the ATS quality criteria.

At least the following variables will be analyzed:

- Vital signs: standard and orthostatic systolic and diastolic BP and HR.
- ECG: HR, PR, QRS, QT and RR intervals, QTcB (Bazett's correction formula calculated as $QT/RR^{1/2}$) and QTcF (Fridericia's correction formula calculated as

QT/RR^{1/3}). ECG parameter values or parameter changes of potential clinical concern will be tabulated.

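### Spirometry MMRM: the continuous ON-state screening value could be added beside TV/OV1, with one sensitivity analysis that uses it alone as baseline

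*Protocol*

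**What the plan says.** Section 12.5 estimates the spirometry changes and the group difference "using a Mixed Model for Repeated Measurements (MMRM) similar to the one used for the efficacy variables". The terms of that model are in Section 12.6: "The model will include visit and the stratification variables (Hoehn and Yahr stage and screening FEV1 and/or FEV1/FVC) as fixed factors", followed by "The baseline value will be used as a covariate".

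Section 12.3 fixes the baseline. In the CVT-301 arm it is the visit of first dosing, which is TV1. For controls, "For the observational cohort, the assessments at TV/OV1 will be used as baseline".

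Section 9.2.1 places randomisation after SV2 and asks sites to leave 7 business days between it and TV1. It adds: "The study is an open-label study, so patients and clinical staff will not be blinded to study group assignment".

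At SV1, Section 10.1.1 says of spirometry that "this must be performed with the patient in the ON state". Inclusion criterion 10 and Section 11.1.6 make that result decide eligibility. At TV/OV1 (Sections 10.3.2.1 and 10.3.2.2) the ON state is preferred but not required. The screening result also defines one randomisation stratum: FEV1 below 60% of predicted or FEV1/FVC below 70%, against neither.

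**The concern.** Each randomised patient has a continuous ON-state FEV1, FVC and ratio recorded before allocation. The model reduces this to a yes/no stratum and carries only TV/OV1 as a continuous spirometry covariate. Two things follow.

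- **Precision.** One baseline session brings its own measurement error. A second reading of the same quantity can average part of that error out and narrow the interval for the group difference in FEV1, the only quantity that Section 12.1 sizes.
- **Allocation knowledge.** Spirometry depends on effort. By TV/OV1 the patient and staff can know the arm, so a shift in one arm at that visit would pass into the adjusted difference. The protocol gives no evidence that such a shift occurs. The point is only that the design allows it.

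**Working it through.** **The plan's own figure.** Completers: 250 × 0.75 = 187.5 and 115 × 0.75 = 86.25, which agree with 188 and 86. Section 12.1 gives no SD, so the 0.121 L statement cannot be checked independently. It can be solved for the SD:

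bound = (z0.975 + z0.90) × SD × √(1/188 + 1/86) = 3.2415 × SD × 0.1302 = 0.4220 × SD

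0.121 / 0.4220 gives SD = 0.287 L (standard error 0.0373 L) for a two-sided 95% interval. The SD is taken as 0.2867 L below.

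**Adding the screening value: assumed session-error model.** Follow-up is Y = T + C + e, TV/OV1 is T + e1 and screening is T + e2. T is the stable level, with assumed SD 0.70 L (variance 0.49). C is the patient's true change. Each e is session error with SD σ, assumed to be 0.10 to 0.18 L. Var(C) = 0.2867² − 2σ², so that the change score has SD 0.2867 L.

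- Residual variance given TV/OV1: Var(Y) − 0.49²/(0.49 + σ²)
- Residual variance given both: Var(Y) − 0.49²/(0.49 + σ²/2)

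For σ = 0.15: Var(C) = 0.0822 − 0.0450 = 0.0372 and Var(Y) = 0.49 + 0.0372 + 0.0225 = 0.5497. TV/OV1 alone: 0.5497 − 0.2401/0.5125 = 0.0812, SD 0.2850. Both: 0.5497 − 0.2401/0.50125 = 0.0707, SD 0.2659.

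| σ (L) | Residual SD, TV/OV1 alone | Residual SD, both | Bound, TV/OV1 alone (L) | Bound, both (L) | Equivalent extra completers |
|---|---|---|---|---|---|
| 0.10 | 0.2864 | 0.2778 | 0.1209 | 0.1172 | 6% |
| 0.15 | 0.2850 | 0.2659 | 0.1203 | 0.1122 | 15% |
| 0.18 | 0.2832 | 0.2559 | 0.1195 | 0.1080 | 22% |

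The last column is the squared ratio of the two SDs minus 1, e.g. (0.2850/0.2659)² − 1 = 0.15.

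**Counting the stratum.** The table leaves out the screening stratum, which the model already holds. Its share was simulated under a different assumption, that all visits correlate equally (r = 0.8 to 0.95), with 5 to 20% of patients in the low stratum. The stratum alone removes about 1 to 5% of the residual variance. The continuous value then removes a further 15 to 23%, for a bound of 0.106 to 0.111 L. Without the stratum the variance ratio is (1 + 2r)/(1 + r)², e.g. 2.8/3.61 = 0.776 at r = 0.9. So the stratum trims the gain but does not use it up.

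**If screening is the weaker predictor.** Two-covariate regression with assumed correlations, scaling the 0.121 L bound:

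| TV/OV1 with follow-up | Screening with follow-up | Screening with TV/OV1 | Variance ratio, both | Bound, both (L) | Bound, screening alone (L) |
|---|---|---|---|---|---|
| 0.90 | 0.88 | 0.92 | 0.907 | 0.1153 | 0.1318 |
| 0.90 | 0.86 | 0.94 | 0.991 | 0.1205 | 0.1417 |
| 0.90 | 0.85 | 0.944 | 1.000 | 0.1210 | 0.1462 |

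The gain falls from 9% of residual variance to nil. Screening alone never beats TV/OV1 alone: with equal correlations it ties at 0.121 L, and otherwise it is worse.

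**Allocation-related shift.** Suppose 0.03 L at TV/OV1 in one arm only (an assumption). The bias in the adjusted difference is 0.03 × the TV/OV1 coefficient.

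- TV/OV1 alone, r = 0.9: 0.03 × 0.90 = 0.027 L, which is 22% of 0.121 L.
- Both, equal correlations: coefficient r/(1 + r) = 0.474, bias 0.014 L.
- Both, correlations as in the three rows above: coefficients 0.589, 0.787 and 0.897, bias 0.018, 0.024 and 0.027 L.
- Screening alone: zero from this source.

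**The case against.** The case for leaving the plan as it is has weight.

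- **Screening spirometry is already in the model.** A reader might infer that the model adjusts for TV/OV1 and nothing else. Section 12.6 does not support that, because the screening stratum is a fixed factor. What stands is that a two-level factor keeps little of the continuous information.
- **Other baseline readings exist.** Section 10.3.2.1 and Appendix 4 show two tests at TV1, on arrival and just before dosing, against one at OV1. Spirometry is also done at the baseline DLco visit. Section 10.1.2 puts that visit before randomisation, while the synopsis asks only that it precede the first treatment or observational visit. The SV1 ON-state test remains the reading that is clearly pre-randomisation, has a mandatory motor state and is taken in the same way in both arms.
- **The bias is conjecture.** Section 11.1.6 provides a central over-read for acceptability and repeatability, which limits effort effects without excluding them. All follow-up tests are open-label too, and no choice of baseline changes that.
- **The gain rests on assumptions.** SV1 is the first study manoeuvre and may predict follow-up less well. The no-gain case is real.
- **The SAP may settle this.** Section 12.5 says only that the model is "similar to the one used for the efficacy variables". Section 12.6 leaves sensitivity analyses to the SAP, and Section 12 lets the SAP supersede the protocol. The SAP was not seen. Even so, Section 12.3 fixes the baseline without deferral, and the minimum sensitivity list in Section 12.6 covers missing data, population and method but not the baseline.
- **The comparison is secondary.** The primary objective in Section 6 is within-arm.

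**Conclusion.** The point holds as a modest improvement. The spirometry model's only continuous spirometry covariate is taken after open-label allocation can be known, and the pre-randomisation ON-state value is kept only as a stratum. Adding the continuous value would move the 0.121 L bound to about 0.108 to 0.117 L under assumed session SDs of 0.10 to 0.18 L and a between-person SD of 0.70 L. The gain is a little less with the stratum counted, and about nil if screening is clearly the weaker predictor. In none of these cases did the addition widen the bound.

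A reader might also infer that one change buys both tighter precision and an allocation-free baseline at no cost. It does not. With both covariates, TV/OV1 keeps a coefficient, so an allocation-related shift is roughly halved at best and hardly reduced at worst. Only screening alone removes it, and that version gains no precision: 0.121 L at best, 0.132 to 0.146 L in the weaker-predictor cases tabulated.

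Nor do the documents support calling the plan wrong. A baseline on the day of first dosing, before the dose, is a workable choice, and no stated figure is contradicted.

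**What to change.** 1. In the spirometry MMRM of Section 12.5, add the continuous ON-state screening value (SV1, or the SV2 repeat where there is one) as a second covariate beside TV/OV1, for each of FEV1, FVC and FEV1/FVC. Keep the stratification factors.
2. Pre-specify one sensitivity analysis in randomised patients with the ON-state screening value alone as baseline. Its outcome should be the follow-up value or the change from screening, so that TV/OV1 does not re-enter through the change score. State beforehand that its interval may be wider.

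**Cost.** One covariate, one extra run and no new measurements. Some screening values may be missing. Roll-over patients from CVT-301-002 and CVT-301-003 were assigned rather than randomised, and their screening spirometry under the previous protocol version is not described. In the analysis restricted to tests meeting ATS criteria, a rejected screening test would drop out. The SAP should say how such patients are handled.
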